10.2 Randomization

Patients will be randomized at study entry. In order to increase the likelihood of good balance between groups, patients will be stratified prior to randomization according to: disease status (relapsed/progressive vs. refractory disease vs. partial response during induction); bone marrow involvement by routine morphology (bone marrow involved at study entry vs. bone marrow free of disease at study entry); age (< 18 years and ≥ 18 years); and receipt of prior ¹³¹I-MIBG (received or not received). The dynamic allocation method of Simon and Pocock will be used to assign patients to one of the 3 MIBG regimens, while balancing across the margins of each of the four stratification variables.¹¹¹

10.3 Response Evaluation

10.3.1 Definition of Evaluable for Response

All patients who are registered onto the study must be assessed for response to treatment, even if there are major protocol treatment deviations or if they are ineligible. Each patient will be assigned one of the following categories (see Section 11):

- a. Complete response
- b. Complete response-Minimal Residual Disease (MRD)
- c. Partial response
- d. Stable disease
- e. Minor response
- f. Progressive disease
- g. Early death from malignant disease
- h. Early death from toxicity
- i. Early death because of other cause
- j. Inevaluable (not assessable, insufficient data, patients off therapy early due to toxicity)
- k. Never received any of the study drugs: ¹³¹I-MIBG, vorinostat, vincristine, or irinotecan.

All eligible, randomized patients will be included in the intent-to-treat analysis of response, according to the randomization outcome. Patients in groups a through c will be classified as responders; patients in groups d through k will be classified as non-responders. In a second analysis, the proportion of responders (patients in groups a through c) will be calculated from the subset of patients who are evaluable for response (as defined in the next paragraph).

In the secondary analysis (per protocol), patients will be considered evaluable for response if they receive ¹³¹I-MIBG that is at least 85% of their prescribed dose (or at least 85% of 1200 mCi protocol maximum dose for patients whose calculated dose exceeds 1200 mCi) plus at least 80% of any prescribed systemic agents (at least 4 days of irinotecan or at least 11 days of vorinostat), or withdraw early due to tumor progression, clinical progression/deterioration, or toxicity. In addition, patients who do not withdraw early must meet the criteria to be adequately evaluated for each of the 3 disease parameters (if they had disease at baseline for that parameter) as described in Section 11, in order to be considered evaluable for response. For each patient not evaluable for response, an additional patient will be enrolled to meet the accrual goals in Section 10.5.

Per Amendment 7A (for clarification): The primary analysis will be a modified intent-to-treat analysis: all eligible, randomized patients who receive any amount of ¹³¹I-MIBG will be included. There will be 2 secondary, additional analyses: an intent-to-treat analysis (all eligible, randomized patients) and a “per protocol” analysis based on all patients who are “evaluable for response” (described above). These will serve as “sensitivity” analyses.

10.3.2 Primary Response Endpoint and Additional Assessments of Treatment Effect

The primary endpoint and analysis will be objective tumor response after one course of therapy based on central review, for all eligible randomized patients who received any amount of ¹³¹I-MIBG (modified intent-to-treat analysis). Two secondary analyses will (a) include all eligible randomized patients and (b) only patients evaluable for response as defined in the paragraph above in section 10.3.1. Patients will undergo complete disease staging (¹²³I-MIBG diagnostic scan, bilateral bone marrow aspirate and biopsy, anatomic imaging with CT or MRI scan, and urine catecholamines) at baseline and then approximately 6 weeks following ¹³¹I-MIBG infusion. Response will be assessed according to NANT response criteria v1.1. These criteria are modified from the International Neuroblastoma Response Criteria¹¹² in that they utilize RECIST 1.1 criteria for measurable tumors¹¹³ and Curie score for MIBG scan response.¹⁰⁶ Patients with an institutional report of complete response, complete response-MRD, partial response, or stable disease will have their response centrally reviewed. An exact logistic regression analysis will be used to compare the 3 arms in terms of response, while controlling for the stratification variables.

For the subset of patients receiving a second course of therapy (enrolled prior to Amendment 7A), the response to the second course of therapy will be reported as well as the overall response to two courses of protocol therapy. Response to the first course will nevertheless be the primary endpoint for study.

Additional endpoints for response to treatment will include response at each site of disease: bone marrow; soft-tissue sites; and ¹²³I-MIBG using NANT response criteria. Progression-free survival and overall survival (summarized with Kaplan-Meier plots) will be additional secondary endpoints.

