11.0 NANT RESPONSE CRITERIA v 1.2

Below are the NANT Response Criteria. Since patients on this study must have MIBG avid tumors, any reference to MIBG non-avid tumors is not applicable.

Overall response will incorporate all three parameters: CT/MRI, MIBG (FDG-PET is substituted for MIBG non-avid tumors), and bone marrow response with overall response defined as outlined in Section 11.6. Response for each parameter and overall response will be reported by the treating site using the criteria below. However, the final statistical analysis of response will utilize responses as graded by central review, using the same criteria below.

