11.6.5 Stable disease (SD)

Response of stable disease for at least one parameter, with response of SD, NI, or SD-NTL for other parameters.

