11.6.6 Minor response (MR)

Complete response, Complete-MRD response, and/or partial response for one parameter (i.e. CT/MRI, MIBG (FDG-PET if MIBG non-avid), bone marrow), with response of stable disease for second parameter and any response other than PD or inevaluable for third parameter.

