13.0 RECORDS AND REPORTING

See separate Data Forms Packet which includes the data submission schedule in the members section on the NANT web site (www.NANT.org)

The following are required to be submitted for all patients entered:

1. Study case report forms, bone marrow reports (including aspirate and biopsy reports), and radiology reports (CT/MRI/MIBG scans). These forms and reports are faxed to the NANT Operations Center at [contact] or sent by email as electronic files to [contact] at the end of each course of therapy (day 43-50 evaluation).
2. For **all** patients on study, CT/MRI and MIBG scans done as baseline tumor evaluation at study entry are required to be submitted into the NANT PACS system or on CD for central review (after approval of NANT Operations Center). Bone marrow slides from study entry may also be requested at the discretion of the Operations Center.
3. For all patients the MIBG scans done at day 43-50 will also be submitted for central review. The MIBG scans should be submitted after day 43-50 evaluation. For patients who report a CR/PR/SD on CT/MRI, scans done at day 43-50 should be submitted for central review after day 43-50 evaluation. In questionable cases, the Operations Center may request CT/MRI scans for central review. It is preferable that scans be submitted electronically into the NANT PACS system. However, when this is not possible scans can be submitted on CD to NANT Operations Center.
4. For patients who report a CR or CR-MRD in bone marrow, bone marrow slides will be submitted from study entry and from day 43-50 evaluation, and from the second bone marrow confirming CR if applicable.

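### Section 10.3.2 leaves site-reported Minor Response off the central-review list, in conflict with a primary endpoint defined by central review for every patient analysed

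*Combined protocol and SAP*

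**What the plan says.** Section 10.3.2 sets the endpoint: "The primary endpoint and analysis will be objective tumor response after one course of therapy based on central review", in the modified intent-to-treat (mITT) population of eligible randomized patients who received any ¹³¹I-MIBG. Section 10.1 selects the regimen with the highest centrally reviewed response rate.

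The same Section 10.3.2 then limits who is reviewed: "Patients with an institutional report of complete response, complete response-MRD, partial response, or stable disease will have their response centrally reviewed". Minor Response and PD are not on that list.

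Section 11.0 carries no such limit. After describing site reporting it states that "the final statistical analysis of response will utilize responses as graded by central review".

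Minor Response is a grade of its own. Section 10.3.1 lists it as item e, separate from stable disease (item d), and classifies as follows: "Patients in groups a through c will be classified as responders; patients in groups d through k will be classified as non-responders". Section 11.6.6 requires CR, CR-MRD or PR in one parameter, "with response of stable disease for second parameter and any response other than PD or inevaluable for third parameter". The stable-disease definition in Section 11.6.5 does not absorb it: "Response of stable disease for at least one parameter, with response of SD, NI, or SD-NTL for other parameters".

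Section 13.0 sets submission by parameter, not by overall grade:
- MIBG: "For all patients the MIBG scans done at day 43-50 will also be submitted for central review".
- CT/MRI: "For patients who report a CR/PR/SD on CT/MRI, scans done at day 43-50 should be submitted for central review". Other CT/MRI scans may be requested if the case is in doubt.
- Marrow: slides are sent if the site reports marrow CR or CR-MRD (item 4).

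**The concern.** A Minor Response already has one parameter at CR, CR-MRD or PR, so one changed reading can turn it into an overall PR. The review list includes SD, which is further from PR, and skips Minor Response. No reason is given.

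The protocol itself expects readers to disagree. Section 2.6.6 describes inter-reader reliability for MIBG scans as often poor and reports that two experienced radiologists agreed on 21 of 25 pilot scans (84%). Section 2.6.8 says it is unknown how well institutional and central Curie scores agree. Section 10.7.6 plans to report how often the MIBG response category would change between them.

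The winner is chosen on the observed rate, and one responder is 1/35 = 2.9 percentage points. Under Section 10.1.1, any decision at the second interim analysis to drop an arm or stop accrual also waits for central review. Whether a site Minor Response can become a central PR should therefore be written down, not inferred.

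**Working it through.** **1. How a Minor Response becomes PR (Sections 11.1.4.2, 11.3, 11.6.3, 11.6.6), and whether the material is sent (Section 13.0).** The cases are illustrative.

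| Site reading | Central reading | Overall grade | Material sent? |
|---|---|---|---|
| CT/MRI PR; Curie 11 from baseline 20, 11/20 = 0.55, SD; marrow not involved | Curie 10, 10/20 = 0.50, PR | Minor Response → PR | Yes, all Day 43-50 MIBG scans |
| MIBG PR; CT/MRI diameters down 28%, SD; marrow not involved | down 30%, PR | Minor Response → PR | Yes, CT/MRI graded SD |
| MIBG PR; CT/MRI not involved; marrow SD above 5% | marrow at or below 5% | Minor Response → PR | No, slides go only for marrow CR/CR-MRD |

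Two of the three routes have their material in hand, and Section 11.3 bases the MIBG endpoint on the central Curie score. What Section 10.3.2 does not supply is a statement that these readings revise a site Minor Response. The third route also lacks the slides.

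**2. Reproducing the plan's figure.** Section 10.5 states 35 per arm for an 80% chance of correct selection when the best arm is 15 points better. Let f_b be the binomial probability for the best arm, and f and F the binomial probability and cumulative probability for each of two equal inferior arms, n = 35. With ties split at random:

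PCS = Σₓ f_b(x) · [F(x−1)² + F(x−1)·f(x) + f(x)²/3]

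The minimum over response rates is 0.826. It is 0.794 if ties are not counted as correct (only the F(x−1)² term) and 0.859 if they are (F(x)²). The stated 80% reproduces. Table A of Appendix VIII at +0.15, with inferior rates 0.10/0.20/0.25/0.30/0.35, gives 94/90/88/86/88%. The fixed-35 calculation with ties counted as correct gives 94.5/89.8/88.2/87.1/86.4%, all within 2 points.

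**3. Size, by assumption.** Let h be the share of true central responders whom the site grades Minor Response and who are never regraded. The observed rate becomes p(1−h). Fixed 35 per arm, ties split, true rates 0.20/0.20/0.35. If every arm is affected, the expected loss is 35·h·(0.20+0.20+0.35) = 26.25h responders.

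| h | Responders lost of 105 (all arms) | PCS, equal loss | PCS, best arm only |
|---|---|---|---|
| 0 | 0 | 0.867 | 0.867 |
| 5% | 1.3 | 0.855 | 0.828 |
| 10% | 2.6 | 0.843 | 0.781 |
| 20% | 5.3 | 0.817 | 0.666 |

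For example, at h = 10% with equal loss the observed rates are 0.18/0.18/0.315. At true rates 0.30/0.30/0.45, h = 0, 5, 10% gives 0.838, 0.824, 0.810 with equal loss and 0.838, 0.783, 0.717 with loss in the best arm only.

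**The case against.** The strongest reply is that Section 11.0 already settles the matter. It has sites report each parameter and the overall response, then puts the final analysis on central grading with no category excepted, and Section 13.0 sends most of what is needed. On that view the sentence in Section 10.3.2 is loose drafting. Much of this stands. It makes the defect a narrow sentence in conflict with a general rule, not a missing rule. It does not remove the conflict, because the narrow sentence sits in the section that defines the primary endpoint and names the reviewed categories one by one.

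Several stronger readings are tempting and are not supported:

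- *A site Minor Response can never be upgraded.* Section 11.0 says otherwise, and the MIBG and relevant CT/MRI scans are collected. Only the marrow route lacks material. It is narrow, since marrow SD with at most 5% tumor already permits overall PR under Section 11.6.3.
- *Review only ever lowers response rates.* Site-reported SD is reviewed and can be upgraded.
- *PD is an equal problem.* PD is not the grade next to PR. Section 11.6.4 lets it rest on one parameter or on clinical judgement alone. MIBG scans of PD patients are submitted, and doubtful CT/MRI can be requested.
- *Narrow margins measure the harm.* The top two arms differ by at most one responder with probability 0.191 at 0.20/0.20/0.35, 0.342 at 0.25/0.30/0.35, and 0.408-0.453 when all arms are equal at 0.30 or 0.20. That shows how fragile a 35-per-arm selection is to any single misclassification, not how often an upgrade is missed. With equal arms no selection is wrong, and the table in Section 10.1.1 scores that case as 1.00. Even if exactly one responder were always lost, and only in the best arm, correct selection at 0.20/0.20/0.35 would go from 0.867 to 0.796.
- *The raw count alone decides.* Section 10.1 adds a proviso on toxicity, tolerability and feasibility, and Section 10.3.2 plans an exact logistic regression controlling for the stratification variables.

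**Conclusion.** Section 10.3.2 is inconsistent with its own definition of the endpoint and with Section 11.0. Read literally, it leaves the grade nearest to PR at its site value while the grades on either side are reviewed. The only gap in material for these patients is marrow graded SD above 5%.

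The size cannot be read from the documents, because they give neither the share of Minor Responses nor a site-central disagreement rate. Under the assumed loss of 5-10% of true responders, correct selection at 0.20/0.20/0.35 falls by 1.2-2.4 points if the loss is equal across arms (0.867 to 0.855-0.843), or by 3.9-8.6 points if it falls only on the best arm (to 0.828-0.781). The documents offer no evidence that the loss would differ by arm, so the larger figures mark a possibility. These values use fixed samples of 35 per arm without the interim rules. The point is a cheap improvement that should be made. It does not challenge the sample size or the stated 80%.

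**What to change.** 1. In Section 10.3.2, replace the list of reviewed categories with a rule that every mITT patient with a Day 43-50 evaluation, explicitly including those with a site-reported Minor Response, has overall response derived from the central readings under Section 11.6.
2. In Section 13.0 item 4, add marrow slides for site Minor Response patients whose overall grade turns on marrow SD above 5%.
3. State that site non-responders without central material, such as PD declared on clinical grounds, keep the site grade and count as non-responders.

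The cost is some extra time for the existing reviewers, mostly on scans already submitted, and retrieval of some marrow slides. The number of cases cannot be stated because the frequency of Minor Response is not given. The first interim analysis went to the DSMB in March 2017 and the protocol is at Amendment 8, so slides will have to be retrieved for some patients already enrolled; otherwise the review rule would differ between earlier and later patients.

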10.4 Toxicity Evaluation

Toxicity is the secondary endpoint of this trial. All patients who begin treatment with vincristine, irinotecan, vorinostat, or ¹³¹I-MIBG will be evaluable for toxicity. Toxicity will be graded using the CTCAE criteria, version 4.0 which can be downloaded from the CTEP home page (<http://ctep.cancer.gov>).

Patients will undergo standard screening for toxicity used in previous NANT ¹³¹I-MIBG studies. All patients who begin study therapy will be evaluable for toxicity. All toxicities will be tabulated and reported according to received treatment arm. Differences in the incidence of toxicities between treatment arms will be assessed using the Fisher’s exact test.

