1.0 GOALS AND OBJECTIVES (SCIENTIFIC AIMS)

Primary Aim:

1.1

To identify the ^{131}I -MIBG treatment regimen associated with the highest overall response rate after one course of treatment on the following three arms: single-agent ^{131}I -MIBG; vincristine / irinotecan / ^{131}I -MIBG; or vorinostat / ^{131}I -MIBG

Secondary Aim:

1.2

To compare the toxicity profiles associated with each of the following three ^{131}I -MIBG treatment regimens: single-agent ^{131}I -MIBG; vincristine / irinotecan / ^{131}I -MIBG; or vorinostat / ^{131}I -MIBG

Exploratory Aims:

1.3

To describe best overall response for patients treated with two courses of therapy, site-specific response of bone marrow, soft tissue, and MIBG-avid lesions as well as overall survival and progression-free survival following each of three ^{131}I -MIBG treatment regimens

1.4

To assess peripheral blood and bone marrow minimal residual disease at study entry and following each of three ^{131}I -MIBG treatment regimens quantified using a neuroblastoma-specific NB 5-gene detection assay (NB5 assay) by TaqMan[®] low density array (TLDA)

1.5

To compare whole body radiation exposure in patients with neuroblastoma treated with each of three ^{131}I -MIBG treatment regimens

1.6

To evaluate peripheral blood lymphocyte γ -H2AX foci levels, expression of a panel of DNA damage response genes in peripheral blood mononuclear cells, plasma Flt-3 ligand, serum amylase, and circulating tumor DNA as markers of radiation exposure, response, and toxicity in patients with neuroblastoma treated with each of three ^{131}I -MIBG treatment regimens

1.7

To evaluate the performance of a computerized MIBG scan scoring system in patients with relapsed or refractory neuroblastoma treated with ^{131}I -MIBG therapy

1.8

To evaluate the association between tumor norepinephrine transporter (NET) protein expression and response to protocol therapy.

1.9

To describe the concordance rate between institutional Curie score and centrally reviewed Curie score in patients with relapsed or refractory neuroblastoma.

1.10

To describe the incidence and severity of sinusoidal obstruction syndrome (SOS) in patients with neuroblastoma who receive ^{131}I -MIBG therapy on this protocol and subsequently receive high-dose chemotherapy with stem cell rescue as part of their clinical care.

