4.0 TREATMENT PROGRAM

4.1 Treatment Overview

Patients will be randomized at study entry to one of three treatment arms.

All patients will undergo disease restaging between Day +43 and +50, 6-7 weeks after ^{131}I -MIBG infusion. Patients enrolling prior to Amendment 7A with at least stable disease to the first cycle can receive a second cycle of therapy, provided they meet stem cell and organ function criteria to proceed to a second cycle (Section 4.6). Patients enrolling with Amendment 7A and later may receive a single cycle.

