4.6 Criteria to Receive a Second Course of Therapy

Patients who meet all of the following criteria at the end of the first course of therapy may proceed to a second course of assigned therapy:

- Enrolled prior to Amendment 7A (patients enrolling with Amendment 7A and later may receive a single course only);
- Adequate stem cells to support a second course per section 3.2.6;
- Organ function meets criteria in section 3.2.10 except:
 - EKG only needs to be repeated prior to course 2 for patients randomized to vorinostat arm; all arms require repeat echocardiogram); and
 - Platelets only need to recover to $\geq 25,000/\mu\text{L}$ (no transfusions for one week prior to CBC documenting platelet recovery to this level);
- No intervening anti-cancer therapy between first course and planned second course;
- Day 1 of planned second course no earlier than Day 43 of first course (minimum 6 weeks between ^{131}I -MIBG infusions);
- No delayed engraftment (section 4.7) or need for dose modification (section 4.8) in first course of therapy;
- Disease status at end of first course of stable disease or better (section 11)
- Cumulative lifetime assigned dose of ^{131}I -MIBG does not exceed 36 mCi/kg at time of planned second infusion on this protocol (based upon assigned dose during that prior therapy; to account for unavoidable dose rounding, maximum previously delivered dose must not exceed 38 mCi/kg).

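### The between-arm toxicity comparison in Section 10.4 is not limited to a course, although access to a second course depends on first-course outcomes that can differ by arm

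*Combined protocol and SAP*

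**What the plan says.** Aim 1.2, the only secondary aim, is "To compare the toxicity profiles associated with each of the following three" regimens, with no reference to a course. Section 10.4 puts it into practice: "All patients who begin study therapy will be evaluable for toxicity", "All toxicities will be tabulated and reported according to received treatment arm", and "Differences in the incidence of toxicities between treatment arms will be assessed using the" Fisher's exact test. It states no course, observation window or exposure adjustment. The interim flag in Section 10.6.4 (two-sided Fisher, 0.10 level, grade 3+ non-hematologic toxicity, about 20 per arm) states none either. Under Section 10.1, patients counted at that interim have completed at least one course, so some may have begun a second.

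Elsewhere the plan does fix the course. The primary aim concerns the "highest overall response rate after one course of treatment on the following three arms". Section 10.3.2 adds that "Response to the first course will nevertheless be the primary endpoint for study". Section 10.7.3 bases the primary biomarker analyses on first-course data.

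Access to a second course is conditional. Section 4.1 says that patients enrolling before Amendment 7A "with at least stable disease to the first cycle can receive a second cycle of therapy". Section 4.6 adds "No delayed engraftment (section 4.7) or need for dose modification (section 4.8) in first course of therapy", recovered organ function (with the EKG repeated only in the vorinostat arm), enough stem cells and a cumulative dose limit. Section 4.8 contains modification rules for vorinostat (4.8.1) and irinotecan (4.8.2) only.

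**The concern.** A per-patient incidence that takes in every course mixes patients observed over one course with patients observed over two. Who gets the second course is settled after randomization, by disease control, engraftment and early toxicity. The dose-modification condition can exclude patients in Arms B and C but has no counterpart in Arm A. The comparison is thus open to two distortions:

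- An arm with more second courses collects more events at the same per-course risk.
- A combination arm that is truly more toxic, and so has fewer second courses, has its excess diluted.

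The second matters more here, because the protocol hypothesizes more toxicity with the combinations, and Section 10.1 makes adoption of the winner subject to toxicity and tolerability. If the course is left unnamed, it can also be chosen after the results are known.

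**Working it through.** The plan gives no sample size, power or alpha for the final toxicity comparison, so there is no stated figure to reproduce. What follows is an illustration under stated assumptions.

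**Inputs from the documents**
- Per-course risk q: 22% to 31%. Section 2.2 reports 22% grade 3 and 9% grade 4 non-hematologic toxicity at 18 mCi/kg; 22 + 9 = 31 if no patient is counted twice. Reading these as per-course risks is an assumption.
- Patients per arm: 35 (Section 10.5).
- Share enrolled before 7A: h = 60/105 = 0.571. The 60-patient interim went to the DSMB on March 15, 2017, and 7A is dated 6-8-2017 (Section 10.1.1), so 60 is a lower bound.

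**Inputs assumed**
- Second-course uptake u among pre-7A patients: 50% v 20%, and 80% v 20% as an extreme.
- Courses independent; uptake unrelated to whether the patient had the event in course 1.
- Two-sided alpha of 0.05 for the final test.

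**Formula.** Any-course incidence = q + (1 − q) × q × u × h. With equal q in two arms, the spurious difference is (1 − q) × q × h × (u1 − u2). A first-course comparison has a true difference of zero.

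**Equal per-course risk, 50% v 20% uptake**
- q = 22%: 0.78 × 0.22 × 0.571 × 0.30 = 0.029 (26.9% v 24.0%).
- q = 31%: 0.69 × 0.31 × 0.571 × 0.30 = 0.037 (37.1% v 33.4%).

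Exact Fisher rejection probabilities at 35 per arm, by full binomial enumeration:

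| Uptake | q | Spurious difference | Rejection, both courses | Rejection, course 1 only |
|---|---|---|---|---|
| 50% v 50% | 22% | 0 | 2.7% | 2.6% |
| 50% v 20% | 22% | 2.9 points | 3.2% | 2.6% |
| 50% v 20% | 31% | 3.7 points | 3.8% | 2.8% |
| 80% v 20% | 22% | 5.9 points | 5.0% | 2.6% |
| 80% v 20% | 31% | 7.3 points | 6.3% | 2.8% |

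**First interim** (20 per arm, all before 7A so h = 1, alpha 0.10, 50% v 20% uptake). The spurious difference is 0.78 × 0.22 × 0.30 = 5.1 points or 0.69 × 0.31 × 0.30 = 6.4 points. This assumes that every second course is complete by then, so it is an upper figure for that uptake. Rejection is 6.8% and 6.9%, against 4.8% and 5.3% for course 1 only.

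**Masking.** Let per-course risk be 22% in Arm A and 40% in a combination arm (assumed), with h = 0.571.
- Course 1 only: difference 40 − 22 = 18.0 points; power 28.7%.
- Uptake 50% in Arm A v 20%: Arm A 0.22 + 0.78 × 0.22 × 0.5 × 0.571 = 26.9%; combination 0.40 + 0.60 × 0.40 × 0.2 × 0.571 = 42.7%; difference 15.8 points; power 21.5%.
- Uptake 80% v 20%: difference 12.9 points; power 14.5%.

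**The case against.** Several points on the other side stand.

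- A reader might infer that the plan orders the courses to be pooled. It does not say so. An unrestricted tabulation is the natural reading of the text, but observations are scheduled by course (Section 7.1) and forms are submitted after each course (Section 13.0), so tabulating by course is open to the analyst.
- A reader might infer that exposure does differ by arm. The documents show only that it can.
- A reader might blame Amendment 7A itself. Randomization is concurrent and dynamically balanced (Section 10.2), so the cutoff alone should not unbalance the arms. Stem cell supply and prior ¹³¹I-MIBG dose are baseline features, and prior ¹³¹I-MIBG is a stratification factor. The conditions that depend on first-course outcome are the source.
- A reader might infer that more objective responses mean more second courses. The requirement is stable disease or better, which is weaker.
- A reader might infer that an arm looks safer for any toxicity that bars its patients from course 2. A patient barred for a first-course event already counts as having that event. The distortion is confined to other toxicity types. That still leaves room: the vorinostat rules turn mainly on grade 4 cytopenias, whereas the interim flag concerns non-hematologic events.
- A reader might apply second-course shares of 50% to 60% to whole arms and obtain differences of 4 to 7 points. That ignores dilution by single-course patients after 7A: 60% of 35 is 21 patients, while only about 20 per arm are known to have enrolled before 7A.
- Selection rests on a judgement about feasibility; no Fisher result decides it.

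It is also fair to say that toxicity of treatment as delivered, over all courses, is a legitimate quantity. But it is not a like-for-like comparison of regimens when the number of courses depends on first-course outcome.

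**Conclusion.** The concern holds in limited form. Section 10.4 does not restrict its formal comparison to a course, and Sections 4.6 and 4.8 make second-course access depend on post-randomization events, one set of which can arise only in Arms B and C. Taken as written, the comparison can create or hide a difference between arms.

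The size is modest: about 3 to 4 points at 50% v 20% uptake with 60 of 105 patients enrolled before 7A, larger if more patients enrolled before 7A, and zero if uptake is equal. Fisher rejection stays below the assumed 5% at that uptake and reaches 5.0% to 6.3% only at 80% v 20%. Loss of a real difference is the greater worry: 18.0 points shrinks to 15.8, or to 12.9 in the extreme case. The uptake figures, the 40% risk, independence between courses and the 0.05 alpha are assumptions; the masking figures also need uptake to be unrelated to the toxicity being compared.

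**What to change.** In Section 10.4, name first-course toxicity as the main between-arm Fisher comparison, and apply the same restriction to the interim flag in Section 10.6.4. Define the first-course period as running from the first dose of any study drug until the start of course 2. For patients without a second course, it runs to the end of the protocol's first-course toxicity follow-up, including the Day 71 platelet engraftment assessment (Section 4.7). Tabulate second-course toxicity separately and descriptively, with the number of patients who began course 2 in each arm.

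A simple cut at Day 50, the end of the restaging window, would not do. Course 2 may start from Day 43 (Section 4.6), so the cut would let in second-course events, and it would miss platelet engraftment judged at Day 71.

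The cost is a sentence or two in each section. No new data are needed, since observations and forms are already organized by course, and the change brings toxicity into line with the response and biomarker analyses. The downside is that second-course events leave the formal test and appear only descriptively.
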